Appendix J Procedures at CRS—Schedule 3: Follow-up on ART

Visit:	80 ¹	81	82	83	84	85	86	87	88	89	90	91 ⁴	92
Days after ART re-initiation:	D0	D14	D28	D42	D56	D70	D84	D112	D140	D168	D196	D280	D364
Weeks after ART re-initiation:	W0	W2	W4	W6	W8	W10	W12	W16	W20	W24	W28	W40	W52
Study procedures													
Complete physical exam													✓
Targeted physical exam	✓	✓	✓	✓	✓	✓	✓	✓	✓	✓	✓	✓	
Concomitant medications	✓	✓	✓	✓	✓	✓	✓	✓	✓	✓	✓	✓	✓
Intercurrent illness/adverse experience	✓	✓	✓	✓	✓	✓	✓	✓	✓	✓	✓	✓	✓
Transmission risk reduction counseling	✓	✓	✓		✓		✓		✓		✓		✓
Contraception status assessment ²	✓	✓	✓	✓	✓	✓	✓	✓	✓	✓	✓	✓	✓
Decision-making assessment	✓						✓			✓			✓
Psychosocial assessment	✓						✓			✓			✓
Social impact assessment	✓	✓	✓	✓	✓	✓	✓	✓	✓	✓	✓	✓	✓
Social impact assessment questionnaire							✓			✓			✓
Specimen collection³	✓	✓	✓	✓	✓	✓	✓	✓	✓	✓	✓	✓	✓

¹ ART re-initiation visit.

² Contraception status assessment is required only for participants who can become pregnant (does not include those persons not of reproductive potential due to having undergone hysterectomy or bilateral oophorectomy [verified by medical records]). Contraception status assessment is not required if participant VL has returned to undetectable.

³ For specimen collection requirements, see [Appendix G](#).

⁴ At an early termination visit for a withdrawn or terminated participant, CRS staff should consider performing procedures specified for Visit 92 (see Section 6.5 and HVTN 805/HPTN 093 SSP for more details).

Appendix K Visit Windows

Visit Windows – Schedule 1: Monitoring ATI

Visit Number	Visit Type	Lower Allowable Window	Lower Target Day	Target Day ⁴ relative to initiation of ATI	Upper Target Day	Upper Allowable Window
01.0 ¹	Screening [for participants not on NNRTIs]	-56	-	-	-	-
	Participants on NNRTIs [ART Switch Participants]	Screening ²	-140	-	-	-
ART Switch ²		-84		-42		-29
ATI Qualification ^{2,3}		-28		-14		0
04.0	Week 0 Initiation of ATI	-	-	0	-	-
05.0	Week 1	-3	-2	7	+2	+3
06.0	Week 2	-3	-2	14	+2	+3
07.0	Week 3	-3	-2	21	+2	+3
08.0	Week 4	-3	-2	28	+2	+3
09.0	Week 5	-3	-2	35	+2	+3
10.0	Week 6	-3	-2	42	+2	+3
11.0	Week 7	-3	-2	49	+2	+3
12.0	Week 8	-3	-2	56	+2	+7
13.0	Week 10	-6	-4	70	+4	+7
14.0	Week 12	-6	-4	84	+4	+7
15.0	Week 14	-6	-4	98	+4	+7
16.0	Week 16	-6	-4	112	+4	+7
17.0	Week 18	-6	-4	126	+4	+7
18.0	Week 20	-6	-4	140	+4	+7
19.0	Week 22	-6	-4	154	+4	+7
20.0	Week 24	-6	-4	168	+4	+14
21.0	Week 28	-13	-8	196	+8	+14
22.0	Week 32	-13	-8	224	+8	+14
23.0	Week 36	-13	-8	252	+8	+14
24.0	Week 40	-13	-8	280	+8	+14
25.0	Week 44	-13	-8	308	+8	+14

26.0	Week 48	-13	-8	336	+8	+14
27.0	Week 52	-13	-8	364	+8	+14
Visit Type A ⁵	Follow-up (Schedule 1: Visit Type A)	-42	-28	Visit Type A will occur every 6 months starting with 3 months after visit 27 continuing up to 3 years of this schedule	+28	+42
Visit Type B ⁵	Follow-up (Schedule 1: Visit Type B)	-42	-28	Visit Type B will occur every 6 months starting with 6 months after visit 27 continuing up to 3 years of this schedule, and then every 3 months thereafter	+28	+42

¹Screening may occur over the course of several contacts/visits up to and including the day of enrollment, as defined in Section 6.1.2. All screening assessments must be done within 56 days of enrollment; for participants on NNRTIs, all screening assessments must be done within 56 days of the ART Switch.

²The ART switch phase will only be performed for participants on NNRTIs.

³Participants must be on the new ART regimen for at least 4 weeks prior to the ATI qualification visit, see Section 6.1.3. The ATI Qualification visit must be at least 28 days from the ART Switch and, if needed, VL interim visits may continue until approximately 12 weeks or until viral suppression has been achieved.

⁴Viral load sample collection should occur as close to the target day as possible and must occur at least 2 days apart (this applies to both scheduled visits and interim visits). See Visit Scheduling and Coding SSP for further details.

⁵Type A and Type B visits must be at least 8 weeks apart.

Visit Windows – Schedule 2: Monitoring ATI with viremia

Visit Number	Visit Type	Lower Allowable Window	Lower Target Day	Target Day ¹	Upper Target Day	Upper Allowable Window
40.0	First visit after confirmed ATI VL ≥ 200 copies/mL	-	-	0	-	-
41.0	Week 1	-3	-2	7	+2	+3
42.0	Week 2	-3	-2	14	+2	+3
43.0	Week 3	-3	-2	21	+2	+3
44.0	Week 4	-3	-2	28	+2	+3
45.0	Week 5	-3	-2	35	+2	+3
46.0	Week 6	-3	-2	42	+2	+3
47.0	Week 7	-3	-2	49	+2	+3
48.0	Week 8	-3	-2	56	+2	+7
49.0	Week 10	-6	-4	70	+4	+7
50.0	Week 12	-6	-4	84	+4	+7
51.0	Week 14	-6	-4	98	+4	+7
52.0	Week 16	-6	-4	112	+4	+7
53.0	Week 18	-6	-4	126	+4	+7
54.0	Week 20	-6	-4	140	+4	+7
55.0	Week 22	-6	-4	154	+4	+7
56.0	Week 24	-6	-4	168	+4	+7
57.0	Week 26	-6	-4	182	+4	+7
58.0	Week 28	-6	-4	196	+4	+7
59.0	Week 30	-6	-4	210	+4	+7
60.0	Week 32	-6	-4	224	+4	+7
61.0	Week 34	-6	-4	238	+4	+7
62.0	Week 36	-6	-4	252	+8	+14
63.0	Week 40	-13	-8	280	+8	+14
64.0	Week 44	-13	-8	308	+8	+14
65.0	Week 48	-13	-8	336	+8	+14
66.0	Week 52	-13	-8	364	+8	+14
Visit Type A ²	Follow-up (Schedule 2: Visit Type A)	-42	-28	Visit Type A will occur every 6 months starting with 3 months after visit 66 continuing up to	+28	+42

				3 years of this schedule		
Visit Type B ²	Follow-up (Schedule 2: Visit Type B)	-42	-28	Visit Type B will occur every 6 months starting with 6 months after visit 66 continuing up to 3 years of this schedule, and then every 3 months thereafter	+28	+42

¹Viral load sample collection should occur as close to the target day as possible and must occur at least 2 days apart (this applies to both scheduled visits and interim visits). See Visit Scheduling and Coding SSP for further details.

²Type A and Type B visits must be at least 8 weeks apart.

Visit Windows – Schedule 3: Follow-up on ART

Visit Number	Visit Type	Lower Allowable Window	Lower Target Day	Target Day¹ relative to ART re-initiation	Upper Target Day	Upper Allowable Window
80.0	ART Re-initiation	-	-	0	-	-
81.0	Week 2	-6	-4	14	+4	+7
82.0	Week 4	-6	-4	28	+4	+7
83.0	Week 6	-6	-4	42	+4	+7
84.0	Week 8	-6	-4	56	+4	+7
85.0	Week 10	-6	-4	70	+4	+7
86.0	Week 12	-6	-4	84	+4	+14
87.0	Week 16	-13	-8	112	+8	+14
88.0	Week 20	-13	-8	140	+8	+14
89.0	Week 24	-13	-8	168	+8	+14
90.0 ¹	Week 28	-13	-8	196	+8	+14
91.0 ¹	Week 40	-42	-14	280	+14	+42
92.0 ¹	Week 52	-28	-14	364	+14	+42

¹There must be at least 8 weeks between visits 90.0 and 91.0, and visits 91.0 and 92.0.

1 LIST OF ABBREVIATIONS AND ACRONYMS

AE	Adverse Experience
AMP	antibody mediated prevention
bnAb	broadly neutralizing antibody
ATI	Analytical Treatment Interruption
ART	Antiretroviral Therapy
DSMB	Data and Safety Monitoring Board
FSR	Final Study Report
PrEP	Pre-exposure Prophylaxis
RSC	Regulatory Support Center
SAE	Serious Adverse Event
SAP	Statistical Analysis Plan
SSP	Study Specific Procedures

2 OVERVIEW

The following describes the Statistical Analysis Plan (SAP) for the analysis of safety data from HVTN **805/HPTN 093** for Data and Safety Monitoring Board (DSMB) reports and the Final Study Report (FSR) for Safety.

3 PROTOCOL SUMMARY

Full title:	Antiretroviral analytical treatment interruption (ATI) to assess immunologic and virologic responses in participants who initiated ART in early HIV infection after having received VRC01 or placebo in HVTN 703/HPTN 081
Short title:	HVTN 805/HPTN 093
Sponsor:	NIAID Division of AIDS
Conducted by:	HIV Vaccine Trials Network (HVTN) and HIV Prevention Trials Network (HPTN)
Protocol chairs:	[name], MPH; [name]; [name], MSc
Sample size:	16 - 61
Study population:	HVTN 703/HPTN 081 participants living with HIV who met criteria for transition to Schedule 2 or Schedule 3 in that trial
Study design:	An exploratory study of participants living with HIV undergoing an analytical treatment interruption after early initiation of antiretroviral therapy (ART) following HIV

acquisition in HVTN 703/HPTN 081, where they received VRC01 or placebo infusions

- Study duration:** Study duration is potentially indefinite for a participant maintaining extended viral control during ATI. Study duration for most participants is expected to be 13-18 months. The maximum anticipated duration for any participant is expected to be approximately 2½ to 3 years.
- Study products:** None. Drugs for ART and for pre-exposure prophylaxis (PrEP) will not be provided by the study or paid for using sponsor funds. Access to external funding sources for PrEP and ART provision is available and is detailed in the HVTN 805/HPTN 093 Study Specific Procedures (SSP).
- Primary hypotheses:** Individuals who initiated ART early in HIV infection in HVTN 703/HPTN 081 will suppress plasma viremia and maintain CD4+ T-cell counts longer during ATI than historical cohorts (ie, SPARTAC African and non-African cohorts described in Gossez et al (1) comprising individuals who initiated ART early in HIV infection without other interventions).
- Individuals who initiated ART early in HIV infection and also received VRC01 within 8 weeks before or after acquiring HIV in HVTN 703/HPTN 081 will suppress plasma viremia and maintain CD4+ T-cell counts longer during ATI than those who initiated ART early in HIV infection and received placebo within 8 weeks before or after acquiring HIV in HVTN 703/HPTN 081.
- ATI will be safe and well-tolerated in individuals who acquired HIV during their participation in HVTN 703/HPTN 081.
- Primary objectives:** To evaluate the effect of early ART initiation, with or without having received VRC01 in the immediate pre-HIV acquisition period and/or during early infection, on the time to meeting ART re-initiation criteria in participants undergoing ATI
- To evaluate the safety of ATI among HVTN 805/HPTN 093 participants
- Secondary hypotheses:** Individuals who initiated ART early in HIV infection and also received VRC01 within 8 weeks before or after acquiring HIV in HVTN 703/HPTN 081 will have

enhanced cellular and humoral responses compared with those who initiated ART early in HIV infection and received placebo within 8 weeks of acquiring HIV in HVTN 703/HPTN 081.

Individuals who initiated ART early in HIV infection and also received VRC01 within 8 weeks before or after acquiring HIV in HVTN 703/HPTN 081 will have more limited viral reservoirs, before and after ATI, than those who initiated ART early in HIV infection and received placebo within 8 weeks of acquiring HIV in HVTN 703/HPTN 081.

Secondary objectives: To evaluate the effect of early ART initiation, with or without having received VRC01 in the immediate pre-HIV acquisition period and/or during early infection, on the development of anti-HIV immune responses and on the potential association of those immune responses with time to meeting criteria for ART re-initiation in participants undergoing ATI

To evaluate the effect of early ART initiation, with or without having received VRC01 in the immediate pre-HIV acquisition period and/or during early infection, on viral load in participants undergoing ATI

To evaluate the effect of early ART initiation, with or without having received VRC01 in the immediate pre-HIV acquisition period and/or during early infection, on HIV reservoir size before and after ATI, and whether HIV reservoir measurements are associated with time to meeting criteria for ART re-initiation in participants undergoing ATI

[figure not shown]
3.1 Précis

While plasma viremia rebounds rapidly in most chronically HIV-infected individuals upon cessation of therapy, early initiation of ART after HIV diagnosis has been associated with later ART-free virologic control in individuals known as “post-treatment controllers” (PTCs). Similarly, preclinical (eg, murine, nonhuman primate [NHP]) and clinical evidence suggest that the presence of broadly neutralizing anti-HIV-1 antibodies (bnAbs), even at a concentration, or with a neutralization sensitivity profile, insufficient to prevent HIV acquisition, may nevertheless modulate the autologous response to HIV infection in ways that help set the stage for later durable virologic control. There is also evidence suggesting that early ART initiation and the presence of bnAbs at the time of or soon after HIV infection may be capable of limiting the establishment of and decreasing the size of viral reservoirs. Whether and how these effects might act together to support durable viral control, and what biomarkers may predict such control, is unknown.

The Antibody Mediated Prevention (AMP) studies HVTN 704/HPTN 085 and HVTN 703/HPTN 081, phase 2b studies assessing the ability of the CD4 binding site bnAb VRC01 to prevent HIV-1 infection, provide a unique opportunity to assess the impact of these hypothesized effects. The AMP studies currently have the only cohort of HIV-1–infected individuals who were diagnosed soon after acquisition, who initiated ART relatively soon after diagnosis, and a subset of whom had bnAb present at or near the time of infection. A pause in antiretroviral treatment—that is, an ATI—is the only way to determine whether early ART initiation with and without VRC01 circulating around the time of HIV acquisition, results in blunted, delayed, or absent viral rebound following discontinuation of ART, or subsequent immune control of any rebound that may be observed. If such an impact is observed, ATI is also the best means of assessing mechanisms and identifying predictive biomarkers of that impact through assessment of innate, cellular, and humoral markers along with characterization of the viral reservoir. Extensive virologic, immunologic, and safety monitoring will be conducted, and the trial has been formulated for consistency with recent consensus guidelines on the design and conduct of ATI studies (2, 3), particularly with respect to risk mitigation.

The study schema is shown below.

3.2 Schema

	SCREEN	PRE-DISCONTINUE ART	SCHEDULE 1			SCHEDULE 2			PRE-REINITIATE ART	SCHEDULE 3		
			ATI WEEKS 0-8	ATI WEEKS 10-24	ATI WEEKS 28-52 ¹	ATI + Viremia WEEKS 0-8	ATI + Viremia WEEKS 10-36	ATI + Viremia WEEKS 40-52 ²		FOLLOW UP ON ART WEEKS 0-12	FOLLOW UP ON ART WEEKS 12-28	FOLLOW UP ON ART WEEKS 40-52
Plasma HIV RNA	✓	✓	WEEKLY	Q2 WEEKS	Q4 WEEKS	WEEKLY	Q2 WEEKS ³	Q4 WEEKS	✓	Q2 WEEKS	Q4 WEEKS	Q12 WEEKS
CD4+ & CD8+ T cell counts	✓	✓	Q2 WEEKS	Q4 WEEKS	Q8 WEEKS	Q2 WEEKS	Q4 WEEKS ⁴	Q8 WEEKS	✓	Q4 WEEKS	Q8 WEEKS	Q12 WEEKS
Hematology & Chemistries	✓	✓	Q4 WEEKS		Q8 WEEKS	Q4 WEEKS		Q8 WEEKS	—	Q4 WEEKS	Q12 WEEKS	Q12 WEEKS

¹ QUARTERLY FOLLOW-UP VISITS MAY CONTINUE BEYOND WEEK 52 FOR PARTICIPANTS WHO DO NOT MEET CRITERIA FOR TRANSITION TO SCHEDULE 2.

² QUARTERLY FOLLOW-UP VISITS MAY CONTINUE BEYOND WEEK 52 FOR PARTICIPANTS WHO DO NOT MEET CRITERIA FOR ART RE-INITIATION.

³ OR WEEKLY FOR WEEKS 10-24, IF VL ≥ 200 copies/mL

⁴ OR Q2 WEEKS FOR WEEKS 10-24 IF VL ≥ 200 copies/mL

* For ART re-initiation criteria, see Section 3.3.3.

4 SAFETY OBJECTIVES AND ENDPOINTS

Primary objectives and endpoints

Primary objective 1

- To evaluate the effect of early ART initiation, with or without having received VRC01 in the immediate pre-HIV acquisition period and/or during early infection on the time to meeting ART re-initiation criteria in participants undergoing ATI

Primary endpoint 1

- Time to meeting criteria for ART re-initiation
- Frequency of sustained post-treatment HIV control, defined as ≥ 24 weeks off ART without meeting ART re-initiation criteria

Primary objective 2

- To evaluate the safety of ATI among HVTN 805/HPTN 093 participants

Primary endpoint 2

- Laboratory measures of safety, adverse events (AEs), SAEs, and rates of discontinuation

Secondary objectives and endpoints

Secondary objective 2

- To evaluate the effect of early ART initiation, with or without having received VRC01 in the immediate pre-HIV acquisition period and/or during early infection on viral load in participants undergoing ATI

Secondary endpoint 2

- Cumulative incidence of participants with viral load ≥ 200 at weeks 8, 16, and 24

Secondary objective 3

- To evaluate the effect of early ART initiation, with or without having received VRC01 in the immediate pre-HIV acquisition period and/or during early infection on HIV reservoir size before and after ATI, and whether HIV reservoir measurements are associated with time to meeting criteria for ART re-initiation in participants undergoing ATI

Secondary endpoint 3

- Frequency of CD4+ T cells carrying intact and/or total pro-viral HIV DNA, replication competent virus, and/or cell-associated HIV RNA

5 COHORT DEFINITION

Participants for this trial will be recruited from among former HVTN 703/HPTN 081 (NCT02568215) study participants who met criteria for transition to Schedule 2 or Schedule 3 in that study and who meet the following inclusion/exclusion criteria that are specified in protocol section 5.

6 RANDOMIZATION

This study is not randomized. Outcomes will be compared using randomized treatment assignment from HVTN 703/HPTN 081.

7 BLINDING

Although this study is not randomized, and study product is not administered, precautions have been taken to protect the integrity of the ongoing HVTN 703/HPTN 081 study.

Participants eligible for screening and enrollment into this study are a subset of all HVTN 703/HPTN 081 HIV-infected participants. Participant recruitment lists are restricted to study staff who already have knowledge of HVTN 703/HPTN 081 HIV-infected participants (details in the HVTN 805/HPTN 093 SSP). HVTN 703/HPTN 081 participant identifiers were masked in this study's database until HVTN 703/HPTN 081 was fully completed and unblinded. Unlike other HVTN studies in which enrollment data is available to all HVTN members, enrollment data for this study are restricted to study team members.

8 SAMPLE SIZE

We calculate the expected trial sized under different scenarios for the percentage of enrolled participants out of the total number of endpoint infected cases from HVTN 704/HPTN 085; scenarios include 25%, 50%, and 75%. Eligible placebo recipients will be capped such that the overall placebo to VRC01 recipient ratio of enrolled participants is at most approximately 1:1. Given that the parent HVTN 704/HPTN 085 study was randomized at a 1:2 placebo to VRC01 ratio, we would only expect to cap the number of eligible placebo recipients if prevention efficacy (PE) exceeds 50%. Given this constraint, along with an assumption of a common prevention efficacy at each dose (PE10 and PE30), the expected trial size will depend on different levels of PE. Under the null hypothesis (PE10 = PE30 = 0%), the total expected number of endpoint infections among placebo recipients is 26 and VRC01 recipients is 55 (Table 4-3 in the parent protocol HVTN 704/HPTN 085); therefore, we assume a trial size of 7, 13 or 20 placebo recipients and 14, 28, or 41 VRC01 recipients depending on the enrollment ratio. Under the alternative hypothesis (PE10 = PE30 = 60%), the total expected number of endpoint infections among placebo recipients is 37 and VRC01 recipients is 30 (Table 4-3 in the parent protocol); therefore, under the different enrollment ratio scenarios, we assume a trial size of 8, 15, or 23 placebo recipients and an equal number of VRC01 recipients so as not to exceed a 1:1 ratio. These six sample size scenarios represent estimated upper and lower bounds for sample size given the expected number of endpoint infections under the null and alternative hypotheses respectively, as well as various scenarios for the percentage of eligible participants who will ultimately enroll in HVTN 804/HPTN 095.

Sample size considerations for time to ART re-initiation criteria (primary objective 1)

Using data from the placebo arm of a therapeutic vaccine study which enrolled early treated patients (80), we modeled the time T (in weeks) to meet re-initiation criteria as a Weibull

distribution with survival function $P(T > t) = \exp[-(\lambda t)^p]$, where $\lambda = \exp(-2.932) = 0.053$ and $p = 2.014$. From these parameters, we estimated the median time to meet re-initiation criteria as 15.6 weeks in the AMP placebo recipients. We can express the treatment effect in terms of either the hazard ratio θ or the factor β by which treatment increases the median time to meet re-initiation criteria; β and θ are related by $\beta = \theta - 1/p$.

We model censoring of time to re-initiation criteria using an exponential model and a maximum follow-up time of 72 weeks, where follow-up is censored at a rate of 20% per year due to either study termination or re-initiation of ART before reaching the re-initiation criteria. Simulating 10,000 trials based on these models of time to re-initiation criteria and censoring, we computed power using a log rank test with alpha equal to 0.05. Power for a 40%, 50%, 60%, and 70% reduction in hazard under different enrollment rate and prevention efficacy scenarios are shown in Table 4-1. These hazard reductions correspond to 29%, 41%, 58%, and 82% increases in the median time to meet re-initiation criteria. Therefore, if VRC01 increases the median time to re-initiation criteria 58% and the enrollment rate is 50%, then under the parent study null hypothesis power to detect a difference in time to re-initiation criteria is 72% while under the alternative hypothesis power is 62%.

Table 4-1 Power under different prevention efficacy results, different enrollment rates and different treatment effects, expressed as either reduction in hazard or percent increase in median time to meet re-initiation criteria

Enrollment Rate		Null hypothesis			Alternative hypothesis			
		25%	50%	75%	25%	50%	75%	
Expected number of placebos		7	13	20	8	15	23	
Expected number of VRC01		14	28	41	8	15	23	
Reduction in hazard	% Increase in median time to meet re-initiation criteria							
	40%	29%	20%	32%	44%	16%	26%	37%
	50%	41%	31%	50%	67%	24%	42%	58%
	60%	58%	46%	72%	89%	36%	62%	81%
	70%	82%	65%	91%	98%	54%	83%	96%

Sample size considerations for safety (primary objective 2)

The goal of the safety evaluation for this study is to identify safety concerns associated with ATI. The ability of the study to detect serious adverse events (SAEs) (see protocol Section 4.2.4.1) can be expressed by the true event rate above which at least 1 SAE would likely be observed and the true event rate below which no events would likely be observed. Under the enrollment rate and PE scenarios described in protocol Section 4.1, Table 4-2 shows the true event rate such that there is a 90% chance of observing at least 1 event (or no events) among three groups; 1) the placebo recipients only, 2) the VRC01 recipients only, or 3) all enrolled participants.

Table 4-2 True event rates above which at least 1 SAE (or below which no events) would likely be observed in a group of size n participants. Event rates are computed separately for various values of n given by the range and midpoint for the estimated number of participants among 3 groups; 1) the placebo recipients only, 2) the VRC01 recipients only, or 3) all enrolled participant based on the enrollment scenarios described in Section 4.1.

n	Placebo recipients			VRC01 recipients			All enrolled		
	7	15	23	8	25	49	16	38	61
At least 1 event	28.0%	14.2%	9.5%	25.0%	8.8%	4.6%	13.4%	5.9%	3.7%
No events	1.5%	0.7%	0.5%	1.3%	0.4%	0.2%	0.7%	0.3%	0.2%

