4.1 Estimated accrual

Recruitment will target participants who received VRC01 or placebo and became HIV-infected during participation in HVTN 703/HPTN 081.

We calculate the expected trial size under different scenarios for the percentage of enrolled participants out of the total number of endpoint infected cases from HVTN 703/HPTN 081; scenarios include 25%, 50%, and 75%. Given an assumption of a common prevention efficacy at each dose (PE10 and PE30), the expected trial size will depend on different levels of PE. Under the null hypothesis (PE10 = PE30 = 0%), the total expected number of endpoint infections among placebo recipients is 26 and VRC01 recipients is 54 (Table 4-3 in the parent protocol HVTN 703/HPTN 081); therefore, we assume a trial size of 7, 13, or 20 placebo recipients and 14, 27, or 41 VRC01 recipients depending on the enrollment ratio. Under the alternative hypothesis (PE10 = PE30 = 60%), the total expected number of endpoint infections among placebo recipients is 35 and VRC01 recipients is 28 (Table 4-3 in the parent protocol); therefore, under the different enrollment ratio scenarios, we assume a trial size of 9, 18, or 26 placebo recipients and 7, 14, or 21 VRC01 recipients. These 6 sample size scenarios represent estimated upper and lower bounds for sample size given the expected number of endpoint infections under the null and alternative hypotheses respectively, as well as various scenarios for the percentage of eligible participants who will ultimately enroll in HVTN 805/HPTN 093.

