4.1.2 Sample size considerations for safety

The goal of the safety evaluation for this study is to identify safety concerns associated with ATI. The ability of the study to detect SAEs (see Section 4.2.3.1) can be expressed by the true event rate above which at least 1 SAE would likely be observed and the true event rate below which no events would likely be observed. Under the enrollment rate and PE scenarios described in Section 4.1, Table 4-2 shows the true event rate such that there is a 90% chance of observing at least 1 event (or no events) among three groups; 1) the placebo recipients only, 2) the VRC01 recipients only, or 3) all enrolled participants.

Table 4-2 True event rates above which at least 1 SAE (or below which no events) would likely be observed in a group of size *n* participants. Event rates are computed separately for various values of *n* given by the range and midpoint for the estimated number of participants among 3 groups; 1) the placebo recipients only, 2) the VRC01 recipients only, or 3) all enrolled participant based on the enrollment scenarios described in Section 4.1.

n	Placebo recipients			VRC01 recipients			All enrolled		
	7	17	26	7	24	41	16	39	61
At least 1 event	28.0%	12.7%	8.5%	28.0%	9.1%	5.5%	13.4%	5.7%	3.7%
No events	1.5%	0.6%	0.4%	1.5%	0.4%	0.3%	0.7%	0.3%	0.2%

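### SAP section 8 carries another trial's sample-size text, including a 1:1 placebo cap the protocol lacks, and its Table 4-2 uses a VRC01 group of 49 that no scenario produces

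*SAP*

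**What the plan says.** SAP sections 3, 5, 6 and 7 describe HVTN 805/HPTN 093 with parent HVTN 703/HPTN 081. SAP section 8 instead draws its scenarios "out of the total number of endpoint infected cases from HVTN 704/HPTN 085" and closes with the participants "who will ultimately enroll in HVTN 804/HPTN 095".

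On allocation, SAP section 8 says "Eligible placebo recipients will be capped such that the overall placebo to VRC01 recipient ratio of enrolled participants is at most approximately 1:1". It adds that, given the parent's 1:2 randomisation, "we would only expect to cap the number of eligible placebo recipients if prevention efficacy (PE) exceeds 50" percent. Protocol 4.1 has no such rule. Under the alternative hypothesis it says "we assume a trial size of 9, 18, or 26 placebo recipients and 7, 14, or 21 VRC01 recipients". Protocol section 5, to which SAP section 5 refers for eligibility, contains no cap either.

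For safety, SAP section 8 introduces its Table 4-2 with the words "Under the enrollment rate and PE scenarios described in protocol Section 4.1". The group sizes it prints are placebo 7, 15, 23; VRC01 8, 25, 49; all enrolled 16, 38, 61. Protocol Table 4-2 (section 4.1.2) prints placebo 7, 17, 26; VRC01 7, 24, 41; all enrolled 16, 39, 61.

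**The concern.** Two governing documents give different planned sizes and a different enrolment rule for the same study. The wrong trial names would be a cosmetic slip if the figures matched, but they do not.

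The cap matters most because it is a rule about whom to enrol. If it were followed when prevention efficacy is high, eligible placebo recipients would be turned away. They are the control arm for the VRC01 comparison and the only AMP group in the comparison with the SPARTAC historical controls (protocol 4.2.3).

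The VRC01 size of 49 makes the study look better able to detect an SAE in that group than any of its scenarios allows. Safety is a primary objective, and this SAP was written for the DSMB reports and the safety report.

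**Working it through.** **1. Arm sizes.** Multiply expected infections by 25%, 50% and 75% and round to the nearest whole number, halves up.

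| | Infections (placebo/VRC01) | Sizes at 25%, 50%, 75% |
|---|---|---|
| Protocol 4.1, null | 26/54 | 7/14, 13/27, 20/41 |
| SAP 8, null | 26/55 | 7/14, 13/28, 20/41 |
| Protocol 4.1, alternative | 35/28 | 9/7, 18/14, 26/21 |
| SAP 8, alternative, before cap | 37/30 | 9/8, 19/15, 28/23 |
| SAP 8, alternative, after cap | 37/30 | 8/8, 15/15, 23/23 |

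Both documents' printed sizes are reproduced. The SAP's follow correctly from its own counts and cap. Four of six scenarios differ from the protocol: 13/28, 8/8, 15/15 and 23/23.

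**2. When the cap binds.** With 1:2 randomisation, placebo to VRC01 infections are in the ratio 1 : 2(1 − PE). This reaches 1:1 at PE = 50%, as the SAP says, so the cap never binds in the null scenarios.

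**3. Power tables.** Comparing the two Tables 4-1 cell by cell, 13 of 24 agree, nine differ by 1 point and two by 2 points. Both two-point differences are at a 70% hazard reduction under the alternative: 52% against 54%, and 85% against 83%.

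**4. Power if the cap is applied to the protocol's own scenarios.** Inputs, stated in both documents:
- Weibull times with λ = exp(−2.932) and p = 2.014. The median is (ln 2)^(1/p)/λ = 15.6 weeks, as printed.
- Exponential censoring at 20% per year and a 72-week maximum.

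The SAP adds the log-rank test at alpha 0.05. I took it as two-sided, which is not stated, and simulated 40,000 trials per cell. A strict 1:1 reading turns 9/7, 18/14 and 26/21 into 7/7, 14/14 and 21/21. The losses are 2 of 9, 4 of 18 and 5 of 26 placebo recipients (22%, 22%, 19%).

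| Hazard ratio | Sizes | 25% | 50% | 75% |
|---|---|---|---|---|
| 0.4 | protocol (printed 35, 62, 81) | 35.1 | 63.4 | 80.6 |
| 0.4 | capped | 32.3 | 58.6 | 77.3 |
| 0.5 | protocol (printed 23, 42, 57) | 23.2 | 41.9 | 58.0 |
| 0.5 | capped | 21.9 | 38.4 | 54.2 |

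The uncapped rows reproduce the protocol's printed power to within about 1 point. The cap costs 2.8, 4.8 and 3.3 points at HR 0.4, and 1.3, 3.5 and 3.8 points at HR 0.5. The smallest study becomes 7 + 7 = 14, below the stated minimum of 16.

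**5. Table 4-2.** The rate with a 90% chance of at least one event is 1 − 0.1^(1/n). The rate with a 90% chance of none is 1 − 0.9^(1/n).
- n = 49: 4.59% and 0.21%. The printed 4.6% and 0.2% were therefore really computed with 49, and the entry is not a text-extraction fault.
- n = 41: 5.46% and 0.26%, as in the protocol's table (5.5%, 0.3%).
- Placebo maximum: n = 23 gives 9.53%, n = 26 gives 8.48%.

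At a true SAE rate of 4.6%, the chance of at least one event in 41 participants is 1 − (1 − 0.046)^41 = 0.855, not 0.90.

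The SAP table contradicts 49 itself. Its all-enrolled maximum is 61 = 20 + 41, whereas 20 + 49 = 69. Its VRC01 midpoint of 25 fits (8 + 41)/2 = 24.5, whereas (8 + 49)/2 = 28.5.

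**The case against.** The practical effect is small. The SAP limits itself to safety analyses and leaves eligibility to the protocol, so section 8 does not govern enrolment. The overall range, the headline power and the analysis methods are the same in both documents. The cap's cost is hypothetical: it needs PE above 50% and a cap that nothing shows was applied. The SAP says approximately 1:1, so the exact 7/7, 14/14 and 21/21 are one strict reading. In SAP Table 4-2, placebo 7, 15, 23 and VRC01 8 and 25 follow from the SAP's own scenarios, so only 49 is a fresh error. The SAE limits are descriptive, and no formal safety test uses them.

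Most of this stands as a limit on size. It does not remove the inconsistency. Section 8 states the cap as something that will be done, and the reference to protocol section 5 does not cancel it. The SAP ties its Table 4-2 to protocol 4.1, so the placebo sizes are also wrong against the source they name, although they come from the carried-over text and not from a miscalculation. That HVTN 804/HPTN 095 is the companion study in the other AMP population is an inference, since the documents identify only HVTN 704/HPTN 085 as an AMP trial.

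**Conclusion.** The concern holds and should be fixed. SAP section 8 describes the wrong parent and study, gives infection counts and arm sizes that disagree with protocol 4.1, and states an enrolment cap that the protocol lacks. Table 4-2 also contains a separate error, VRC01 n = 49 instead of 41, which understates the SAE limit (4.6% instead of 5.5%).

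The printed power differs by no more than 2 points and no analysis method changes. The weight rests on the unreconciled cap: about a fifth of placebo recipients and roughly 1 to 5 points of power at the hazard ratios checked, conditional on PE above 50%, strict 1:1 application, the protocol's alternative scenarios and a two-sided log-rank test.

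**What to change.** First, have the sponsor state whether a placebo cap was intended for this study.

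- **If not:** delete it. Correct the trial names in SAP section 8 and substitute the infection counts, arm sizes and Tables 4-1 and 4-2 of protocol 4.1. Table 4-2 then reads placebo 7, 17, 26; VRC01 7, 24, 41; all enrolled 16, 39, 61.
- **If so:** add the cap to the protocol and recompute sizes, power and Table 4-2 in both documents. On a strict 1:1 reading the alternative sizes are 7/7, 14/14 and 21/21. The largest placebo group is then 21, with a 90% detection limit of 1 − 0.1^(1/21) = 10.4%, and the minimum study size is 14, with a limit of 1 − 0.1^(1/14) = 15.2%.

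In either case keep the SAP's statement of the power method, 10,000 simulated trials and "we computed power using a log rank test with alpha equal to 0.05", because the protocol does not give it, and add whether the test is two-sided.

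The first route costs edits to the SAP text and two tables, using figures that already exist. The second needs a protocol amendment and a rerun of the existing simulation.
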